Specifically for the Zeiss microscopes, the RESIGHT system can be used. This device is mounted below the microscope, and allows the surgeon to look through a lens which is held by a swing arm just above the surface of the eye. The RESIGHT system is highly integrated within the ZEISS LUMERA/ARTEVO microscopes, which has several ergonomical advantages. Firstly, the microscope automatically changes several settings (illumination, foot pedal control, inverting system, ...) when the RESIGHT is inserted into the field-of-view. Secondly, the focusing can be done with the microscope foot pedal and the system focuses internally whereby the distance between the surgical lens and the cornea remains unchanged.

Since the purchase of our LUMERA 700 (and later on: ARTEVO 800) microscopes, we have been using the RESIGHT system for all our vitrectomy surgeries.

The RESIGHT provides two selectable lenses, the 60D (green one) and the 128D (yellow one).

The yellow lens has lower magnification and more overview to allow good visualization of the periphery. The green lens provides higher magnification for macular surgery but as a consequence offers less overview in the eye. During vitrectomy for macular surgery, the lenses will be switched a few times by dialing the

desired lens in front of the eye. During the vitreous removal and the lasering of the retina, the yellow lens is used. During the macular surgery (e.g. removal of epiretinal membrane or peeling of the inner limiting membrane), the green lens is used.

At present, both RESIGHT lenses are reusable and are cleaned and sterilized (reprocessed) together with the RESIGHT system itself after every surgery. These reusable lenses are validated for 200 reprocessing cycles. We do notice that after a few dozen reprocessing cycles, wear & tear occurs which results in the following observations:

- The lens surface shows scratches from the cleaning process, which deteriorates the surgeons' view.
- The lens surface shows stains, created by leftovers of the cleaning agents used. These stains become permanently “baked” into the lens surface due to the heat from the sterilization process.
- Condensation occurs on the lower surface of the lens (closest to the eye surface), again hindering the surgeon's view.

Picture of RESIGHT wide angle viewing system mounted underneath the ARTEVO microscope.

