#### 1.1.4 3D Viewing

[figure not shown]
The ARTEVO 800 microscope head has two high-resolution (4K) cameras built-in, that allow the projection of a 3D image on a 55 inch screen. The surgeon can choose to perform the surgery using the screen while wearing (passive) 3D glasses. In this surgical mode, the surgeon is not looking through the microscope, but directly on the 3D screen to perform the surgery. However, for surgeons who prefer not to work on the 3D screen, the microscope can be switched to “hybrid” mode where the surgeon looks through the ocular of the microscope while the other people attending the surgery can view the image on the 3D screen. Even in the middle of a procedure, the surgeon can choose to switch between 3D and hybrid mode by simply flipping a button on the microscope. Because of the high sensitivity of the 4K cameras, less light is required compared to traditional oculars. Mainly during retina surgery using endo-illumination, this makes the surgery safer by reducing the incidence of light-toxicity to the retina. Moreover, a smaller numerical aperture (‘diaphragm’) can be used for 3D visualization, which increases the depth-of-field compared to viewing through an ocular.

However, a side-effect of the increased depth-of-field is that scratches / stains / condensation on the

RESIGHT lens surface will be more visible. Hence, a clean optical pathway is mandatory for adequate visualization in 3D surgery.

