## 1.2 Disposable RESIGHT Lenses

These wear & tear disadvantages can be overcome by using disposable lenses mounted on the RESIGHT system. Such disposable lens system compatible with the RESIGHT is already available from a third-party source (Oculus LenZ), but is not implemented in our center because of the high cost. Moreover, this Oculus LenZ is shaped to replace both the high-magnification 60D RESIGHT lens (green) and the wide-field 128D RESIGHT lens (yellow), but this does not offer the same optical quality compared to each of these two separate lenses.

ZEISS has designed a series of disposable lenses that are compatible with the RESIGHT system.

1. WIDE-ANGLE LENS (Yellow)
2. MACULA LENS (Green)
3. ULTRA WIDE-ANGLE LENS (Purple)

All three lenses are created from the same material:

- Optical part: PMMA (poly-methyl methacrylate = "plexiglas")
- Holder arm: ABS20 (acrylonitrile butadiene styrene; same material as Lego bricks)
  - MACULA LENS: color green 509
  - WIDE-ANGLE LENS: color yellow 408
  - ULTRA WIDE-ANGLE LENS: color traffic purple 854

These materials are commonly used for medical applications and can be sterilized in ethylene-oxide without deformation, opacification or leaching.

I had the opportunity to test these prototypes of these lenses on *in vivo* pig eyes in lab conditions. From these preliminary tests, the following conclusions were drawn:

1. The disposable wide-angle lens has the same use as the present reusable yellow lens, but its improved design makes it possible to use this lens for both peripheral work as well as macula surgery.
2. Macula lens: this lens has the same macula surgical use as the present reusable green lens. However, its improved resolution provides comparable or even better performance than a flat contact lens.
3. Ultra-Wide angle lens: this newly designed lens provides the same wide-angle view as a convex contact lens, albeit without any contact with the corneal surface. However, this ultra-wide lens must be kept closer to the corneal surface compared to the yellow lens, hence may condensate more easily.

Apart from the optical improvements, the use of disposable RESIGHT lenses is expected to also overcome the issues that we presently encounter when using the reusable lenses:

- No scratches or stains on the lens surface since a brand-new lens is used in every surgery.

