- Not more (or minimum) condensation of the lens surface of the disposable lens as compared to the reusable lens since each disposable lens will have an intact coating.

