## 2.2 Primary Endpoints

The purpose of this study is to evaluate the intra-operative efficacy of new intra-operative viewing device, more specifically:

[figure not shown]
1. To determine whether the performance of the disposable MACULA LENS is comparable or even better than a flat contact lens, due to its improved resolution. For this purpose, the in-house available Vitreq contact lens will be used.  
This parameter will be determined in the macular surgery study arm only.
2. To determine that the disposable ULTRA WIDE-ANGLE LENS does not condensate / condensates to a lesser extent during surgery.  
This parameter will be determined in both study arms.
3. To determine that the disposable ULTRA WIDE-ANGLE LENS allows for imaging up to ora serrata on human eyes, reducing the need for indenting. This parameter will be determined in the retinal detachment surgery study arm only.
4. To evaluate whether both peripheral vitrectomy as well as macula work are possible with the disposable wide-angle lens. This parameter will be determined in the macular surgery study arm only.
5. To evaluate the amount of fogging that occurs when using the disposable wide-angle lens compared to using the reusable yellow lens.
6. To evaluate whether the amount of light to illuminate the retina is reduced when using any of the disposable lenses compared to the reusable yellow/green lenses. This parameter will be

determined in both study arms.

7. To evaluate whether the disposable lenses show a more natural color representation compared to the reusable yellow and green lenses. This parameter will be determined in both study arms.
8. To evaluate whether the iOCT quality recorded with the disposable macula lens is similar to or better than the iOCT recorded using the green reusable lens. This parameter will be determined in the macular surgery study arm only, where iOCT is being recorded as standard-of-care.

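### Does endpoint 5 (fogging) need the reusable lens's reprocessing count, given that the disposable lens is always new?

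*Combined protocol and SAP*

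**What the plan says.** Endpoint 5 in Section 2.2 reads: "To evaluate the amount of fogging that occurs when using the disposable wide-angle lens compared to using the reusable yellow lens". It sets no age or cycle limit for the reusable lens and, unlike most of the other endpoints, names no study arm.

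The background on the RESIGHT system (Section 1.1.3, under indirect ophthalmoscopy systems) says the reusable lenses "are cleaned and sterilized (reprocessed) together with the RESIGHT system itself after every surgery". It adds: "These reusable lenses are validated for 200 reprocessing cycles". On wear it says: "We do notice that after a few dozen reprocessing cycles, wear & tear occurs". Scratches, stains and condensation on the underside of the lens are the listed results.

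Section 1.2 first describes optical gains of the new lenses. It then continues: "Apart from the optical improvements, the use of disposable RESIGHT lenses is expected to also overcome the issues that we presently encounter" with the reusable lenses. The condensation benefit is explained in one way only: "since each disposable lens will have an intact coating".

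The Synopsis names the current standard-of-care lenses as the comparators. Section 2.1 has old and new lenses mounted together, so that the surgeon switches between them during one operation. It lists better lens design and better resistance to fogging as two items, and says the findings may lead to changes in the disposable lenses.

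The surgeon's form is an attachment (Section 2.3), and Appendix 4 contains only the title of the eCRF export. Section 7 refers analysis detail to a separate SAP. Section 7.2.1 contains no term for lens age.

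**The concern.** The comparison sets a lens with no reprocessing cycles against one that may have up to 200. The protocol itself says wear produces condensation, which is the outcome of endpoint 5. Nothing in the supplied text records, fixes, caps or adjusts for the reusable lens's cycle count. Less fogging with the disposable could therefore reflect its design, its newness or both, and a less worn reusable lens might have done as well. A null result would be unclear in the same way, since matching a nearly new lens differs from matching a heavily used one.

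At stake would be any statement that the design reduces fogging, the use of the result to refine the lenses, and its transfer to centres whose reusable lenses are newer or older. A count that was neither recorded nor recoverable could not be added at the analysis stage.

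**Working it through.** **1. The plan's own figure.** The only planning figure is the sample size: 2 × 60 = 120 eyes, which agrees. No fogging rate, effect size, power or margin is given, so no effect of wear can be computed from the documents. Steps 2 to 4 are illustrations with stated assumptions.

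**2. Can the difference be split?** Write D = design effect + (wear effect per cycle × cycle count c). Assume 30% fogging with the reusable lens and 10% with the disposable, so D = 20 percentage points. The whole of D could be wear if the wear effect per cycle were:

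- c = 25: 20/25 = 0.8 points
- c = 50: 20/50 = 0.4 points
- c = 100: 20/100 = 0.2 points
- c = 200: 20/200 = 0.1 points

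Equally, the whole of D could be design, with no wear effect. There is one observed quantity and two unknown components, so with neither negative the design share runs from 0 to 20 points. More eyes do not help. Approximate unpaired two-sided power at these rates is 79% with 60 observations per lens and 98% with 120, and the split is unidentified at both sizes. This part of the concern is correct.

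**3. How worn might the reusable lens be?** Assume one cycle per operation, k yellow lenses shared equally, all new at the start and used only in the trial, and wear beginning at T = 24 to 48 cycles. Eyes operated on with a worn lens = k × max(0, 120/k − T):

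| k | T = 24 | T = 36 | T = 48 |
|---|---|---|---|
| 1 | 96 (80%) | 84 (70%) | 72 (60%) |
| 2 | 72 (60%) | 48 (40%) | 24 (20%) |
| 3 | 48 (40%) | 12 (10%) | 0 |
| 5 | 0 | 0 | 0 |

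Lenses already past T at the start give 120 of 120. The share is thus anywhere from 0% to 100%. Section 1.1.3 says the centre uses RESIGHT for all its vitrectomies, so trial-only use is unlikely and the true share is probably higher than the table shows.

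**4. How few eyes give significance?** Assume yes/no scoring and a two-sided exact sign test. Six eyes fogging only with the reusable lens and none the other way give p = 2 × (1/2)^6 = 2/64 = 0.031, below the 5% level in Section 7.2.2. Five against none give 2/32 = 0.0625. The calculation holds whatever caused the fogging, so it is not evidence of a wear effect.

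**5. Does the plan need the split?** Endpoint 5 compares two lenses and makes no claim about why they differ. Section 1.2 sets the wear-related benefits apart from the optical ones and rests the condensation benefit on the intact coating alone. Section 2.1 keeps design and fogging resistance apart. For this endpoint, newness is what a disposable lens is meant to supply. The changes foreseen in Section 2.1 concern the disposable lenses, and how much the disposable itself fogs can inform them whatever the state of the reusable lens.

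**6. Would recording the count give the split?** With one reusable lens used only in the trial, the count equals case order minus one, so wear cannot be separated from calendar time or surgeon experience. The low-cycle estimate would rest on 24 to 48 of 120 eyes, with an interval √(120/48) = 1.58 to √(120/24) = 2.24 times as wide as with all eyes, assuming independent eyes. With few lenses the analysis would be descriptive only, and a low-cycle lens is still not an unused one.

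**The case for a change.** The strongest reply is that wear is no remote possibility: the protocol itself names it as a cause of condensation. Logging a lens identifier and a cycle count would add no patients, visits or surgical steps. Section 8 describes the form as a report on the disposable lenses, and Section 2.3 exports only the form's content, so a field missing from the form would not reach the statistician. Section 7.2.4 lets the analysis be settled before data lock, but that cannot restore a count nobody kept. Readers elsewhere would also want to know how worn the comparator was.

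Two things stand. A fogging difference should not be credited to design or assumed to hold against newer or older reusable lenses. Logging the lens identity and count would be a reasonable optional addition if the form lacks them. The rest does not amount to a correction. The form and the separate SAP are not in the supplied text, so the fields may already exist. If they do not, adding them may be a substantial amendment under Section 9.7, for a question that is not among the stated objectives.

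Two extensions are weaker still. Section 1.1.4 says lens defects show more in 3D viewing, but both lenses are viewed in the same eye and nothing suggests that viewing mode follows the lens. For endpoints 6 to 8, an effect of wear is only inferred from scratches and stains.

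**Conclusion.** No change to the plan follows. Endpoint 5 is a fair comparison of a new disposable wide-angle lens with the reusable yellow lens as it is used in routine care, and that conclusion stands without a cycle count. The limit is real but concerns attribution: without the count, the design share of any fogging difference lies anywhere from 0% to 100%, and enrolling more eyes would not narrow it. With the count, the split might still be only descriptive or inseparable from case order.

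This rests on reading endpoint 5 as written, with no claim about mechanism, and on the protocol's own account of the fogging benefit as one of an intact coating. The 24 to 48 cycles, the number of lenses, the fogging rates and the yes/no scoring are assumptions. A report that states the result as a product-in-use comparison stays within what the design supports.

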### 2.3 Design of the Clinical Investigation

Investigator-initiated, academic, mono-center, prospective, interventional case study. No randomization will be performed.

Sixty eyes will be enrolled in two study arms:

- Group 1: 60 eyes that undergo primary vitrectomy surgery for retinal detachment
- Group 2: 60 eyes that undergo macular surgery: pucker, vitreomacular traction or macular hole.

The study duration for the participants starts from the moment the patient is informed.

After the surgical procedure, the surgeon will record the parameters that are required to determine the primary outcomes of the study (§6). These parameters will be recorded in a Formasa form specifically designed for this study: see attached document. No information will be collected in this document that can identify the patients, the only clinical information used is the indication of the surgery (since this impacts the primary outcome parameters collected). After all patients (120 eyes) will be included in the trial, a KWS query will be used to export the Formasa forms. Only the content of these forms will be exported for statistical analysis.

In case a device deficiency occurs (any issue that hinders the surgery when using a disposable RESIGHT lens), it will be recorded in the Device Deficiency form (see attachment). Additionally, any (Serious) Adverse Event resulting from such Device Deficiency will be recorded in the (S)AE form (see attachment).

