## 2 Objectives and Design

### 2.1 Study objectives and hypotheses

This study is designed to obtain more information on the efficacy of the disposable RESIGHT lenses in routine vitrectomy surgery. This information can lead to adjustments to these surgical lenses to further fine tune a device which can be used by other surgeons.

[figure not shown]
Theoretically, both the improved lens design and better resistance to fogging should improve the visualization of the retina hence facilitate the surgery, increasing the surgical safety.

During the surgery, a comparison will be done between the present lenses used (reusable RESIGHT lenses and disposable Vitreq contact lens) and the new disposable RESIGHT lenses. For that purpose, both lenses will be mounted on the rotating arm of the RESIGHT allowing the surgeon to toggle between both lenses during surgery. This toggling takes a few seconds, hence the total surgery time may be extended by ~30 seconds. However, this will most likely not impact patient safety since a vitrectomy surgery typically requires one hour time.

To compare the image generated by the present and the new RESIGHT lenses, both still shots and (short) video recordings will be created during the surgery. For this purpose, the internal camera and recording system of the ARTEVO microscope will be used. This will not have any impact on the surgery duration. Since only the retinal image is recorded, there is no risk of patient recognition on the recorded photos and videos.

Moreover, the Artevo microscope has a function that generates anonymous data export which will protect the patients' identity.

Although there is no contact between the lens and the patient, the lens is touched by the surgeons' glove, hence must be sterile. ZEISS will deliver these lenses pre-sterilized according to the present required standards. ZEISS will provide these lenses packaged and labeled according to their specifications.

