# 8 Data handling

Data handling and data flows for the Investigation are summarized below.

An eCRF will be created on the RedCap platform, containing the following instruments:

- Surgeons' report on the disposable RESIGHT lens(es) used during surgery: same information as recorded in the Formasa form
- Device Deficiency form
- (Serious) Adverse Event form

This platform provides all required functionality, security and traceability to be compliant with a CRF. To pseudonymize the patient data, a sequential data number will be created as study number not containing a link to any patient identification data using in the hospital. A separate file containing the EMR number of each patient linked to the study number (pseudonymized data) will be kept behind the hospital firewall, only accessible by the study personnel involved in this trial.

All documents will be stored safely in confidential conditions. On all clinical investigation- specific documents, other than the signed consent, the participant will be referred to by the clinical investigation participant number/code, not by name.

All clinical investigation documentation will be kept for 25 years from the clinical investigation plan defined end of clinical investigation point. When the minimum retention period has elapsed, clinical investigation documentation will not be destroyed without permission from the sponsor.

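### Endpoint 8 (iOCT quality) reaches the analysis only through the form of the surgeon who operated and knew the lens; the protocol text states no lens-coded reading of the recordings

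*Combined protocol and SAP*

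**What the plan says.** The lens comparison is made within the eye. Section 2.1 mounts the present and the new lens together, "allowing the surgeon to toggle between both lenses during surgery". The same section says that "both still shots and (short) video recordings will be created during the surgery", and gives image comparison as their purpose.

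Section 2.3 sets the data source: "After the surgical procedure, the surgeon will record the parameters that are required to determine the primary outcomes of the study". It then limits the export: "Only the content of these forms will be exported for statistical analysis". Sections 7 and 8 describe a second route, an Excel export from a RedCap eCRF. Its efficacy instrument is the surgeon's "report on the disposable RESIGHT lens(es) used during surgery: same information as recorded in the Formasa form"; the other two instruments cover device deficiencies and adverse events.

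Endpoint 8 in section 2.2, for the macular arm only, asks whether "the iOCT quality recorded with the disposable macula lens is similar to or better than the iOCT recorded using the green reusable lens". Endpoint 7, for both arms, is worded "To evaluate whether the disposable lenses show a more natural color representation compared to the reusable yellow and green lenses".

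Sections 2.3 and 4.3 exclude randomisation, the arms being set by surgical indication. No section of the protocol text gives a viewing order for the lenses, a reader for the recordings, or a step that hides the lens from a reader.

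**The concern.** Image quality is a judgement, and the person judging knows which lens produced the image. The plan does not use the word unmasked, but the inference is safe: the surgeon changes the lenses, section 1.2 gives each disposable lens its own holder colour, and the endpoint 1 comparator is a contact lens on the eye.

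The plan also records a general expectation before any data. Section 2.1 expects better visualisation from the new design, and section 1.2 says of the macula lens that "its improved resolution provides comparable or even better performance than a flat contact lens". If such an expectation colours the ratings, it acts the same way in each eye, and more eyes do not average it out.

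For endpoint 8, equality already meets the aim. The risk is therefore that a true inferiority of the new lens is hidden, or that equality is reported as superiority. The iOCT comparison is also the one best suited to later reading, because the endpoint concerns a recording and not only a live impression.

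**Working it through.** **Tracing the data.** (a) The rating is made by the operating surgeon after surgery (2.3). (b) Export route one is a query of the surgeon's forms, with only their content going to analysis (2.3). (c) Export route two is the eCRF (7 and 8), whose efficacy content equals that form. Both routes end at the same rating. (d) The microscope's anonymous export in 2.1 protects the patient's identity; the text links it neither to the analysis data nor to hiding the lens. So, as written, the recordings can influence the analysis only through what the surgeon enters.

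**The plan's own figure.** The only design number is 120 eyes, and 2 × 60 = 120. No power, effect size, variance or margin accompanies it, so nothing further can be reproduced.

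**Illustration for endpoint 8.** From the documents: 60 eyes (macular arm) and a 5% level. Assumed: an exact two-sided sign test on within-eye preference, tie rate *t*, true untied preference for the new lens *p*, and a shift *d* towards the new lens from knowing its identity. The sign test is not a test named in 7.2.1; it is used because the rating scale is not shown.

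- Untied eyes: M ~ Binomial(60, 1 − *t*).
- For M = m, c(m) is the largest k with 2 × P(Bin(m, 0.5) ≤ k) ≤ 0.05.
- Chance of showing inferiority = Σ P(M = m) × P(Bin(m, *p* + *d*) ≤ c(m)).

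One term, with *t* = 30%: the expected M is 60 × 0.7 = 42, and c(42) = 14 (two-sided level 4.4%). P(Bin(42, *p* + *d*) ≤ 14) is 74.3% at 0.30, 48.1% at 0.35 and 23.6% at 0.40. Summing over all m gives:

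| True *p* | Ties | No shift | 5 points | 10 points |
|---|---|---|---|---|
| 30% | 0% | 83.8% | 55.9% | 25.7% |
| 30% | 30% | 70.8% | 44.3% | 20.9% |
| 30% | 50% | 52.5% | 30.3% | 14.2% |
| 40% | 30% | 20.9% | 7.2% | 1.8% |

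**Imperfect masking.** Suppose bias acts only where the reader recognises the lens. A 10-point shift then becomes 10 × the share recognised. At 30% ties and *p* = 30%:

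- always recognised: 10 points, 20.9%
- recognised in half: 5 points, 44.3%
- recognised in a quarter: 2.5 points, 57.8%
- never recognised: 0 points, 70.8%

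**The case against.** **The missing documents may answer it.** The surgeon's form (2.3), the eCRF (Appendix 4) and the study-specific SAP (section 7) are where scales, image scoring and order fields would normally sit. The surgeon completes the form after surgery and might consult the recordings. This stands: the point concerns what the protocol text states, and a citation to the form or SAP would settle it.

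**The size is assumed.** Bias, tie rate, true inferiority and test are all outside the documents. This also stands. The table shows sensitivity; it does not estimate the bias in this trial.

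**The direction is not documented for iOCT.** Sections 1.2 and 2.1 speak of resolution, field of view, fogging and visualisation in general, not of iOCT or colour. For the ultra-wide lens, section 1.2 expects that condensation may come more readily, which runs against the new lens. A reader might infer that the plan shows a bias towards the new lens on every endpoint; the text does not support that.

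**Masking will leak.** Lens features may be recognisable in the image, and the readers may share the expectation. The number of surgeons is not stated; a sole surgeon would re-read his or her own cases. This limits the gain but does not remove it, unless the lens is always recognised.

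**This is a small, single-centre case study meant to inform lens adjustment, and the operator cannot be masked.** True, and it argues for a narrow remedy. It does not argue against scoring recordings the endpoint already relies on.

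**Conclusion.** The gap is real in the protocol text and matters most for endpoint 8. The operating surgeon's rating is the only stated route to analysis, although the endpoint is about recordings that could be read without lens identity. Under the assumptions above (60 eyes, 30% ties, true preference 30%), the chance of showing an inferior lens to be inferior drops from 71% to 44% or 21% for a 5- or 10-point shift. With a smaller true inferiority (40%), it is low even without bias.

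Three stronger readings are tempting and not supported.

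- **That a coded reading would repair endpoint 7.** Section 1.1.4 allows the surgeon to work through the ocular, so a camera still need not be what the surgeon saw, and the live rating should stay primary. A supporting reading leaves the error of that primary rating unchanged. The size of that error is also uncertain. With no true difference, 30% ties and untied ratings tipped to 55/45 or 60/40, the same kind of test is significant in 12% or 41% of trials at 120 eyes, but 7.5% or 21.0% at 60. Section 2.2 says both arms without saying they are pooled.
- **That viewing order has biased the comparison.** No order is stated, but nothing in the documents shows a drift between views, so a prescribed order is not justified.
- **That the sponsor has no image-reading plan at all.** The unseen form and SAP prevent that conclusion.

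This is a worthwhile, inexpensive improvement; it does not show that the trial's comparison is invalid.

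**What to change.** 1. **Endpoint 8.** State in 2.2, 2.3 and section 8 that the analysed score comes from the iOCT recordings with lens identity removed, shuffled across eyes and scored after the last surgery by the existing study surgeon(s). Where there is more than one surgeon, the scorer should not have operated on that eye. Make this score primary and the live rating supportive. Add the score to the eCRF and to the export statement in 2.3. Asking the scorer to guess the lens would show how well the masking worked.
2. **Viewing order.** Record the actual order in which the lenses were viewed and show results by order. No prescribed list is needed.
3. **Endpoint 7, optional.** Add the same coded reading of the existing stills as a supporting analysis only.
4. **Limitation.** State that endpoints 1, 2 and 5 and the primary rating of endpoint 7 are live-scored by an operator who knows the lens.
5. **Timing.** Settle items 1 and 2 before the first surgery, or cite the form or SAP section that already covers them. Section 7.2.4 allows the statistical plan to be agreed as late as just before data lock. A coded reading of existing recordings could still be added then; a record of viewing order or a missing recording through one of the lenses could not.

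The cost is scoring time and a few eCRF fields, with no added eyes or visits. Each eye needs a usable iOCT recording through both lenses, which endpoint 8 already presupposes. Masking will be imperfect, and nothing is gained if the lens is always recognised.

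As a separate clerical matter, the flowchart's row for randomisation should be reconciled with 2.3 and 4.3.
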